## 4.5. Dose Adjustment Algorithm

Between Weeks 2 to 52, the dose of daprodustat should be adjusted if required (see Section 4.6), one dose step at a time, to achieve/maintain a Hgb within the target range of 10 to 12 g/dL.

## 4.5.1. Dose Adjustment Algorithm in the 12 to <18 Years Age Group

As exposure in the oldest age group (12 to <18 years) is predicted to be the same as adults, the dose adjustment algorithm will be similar to adults, see Figure 3. The dose in this study (for both the ND/D sub-trials), as in the adult Phase 3 program, cannot exceed 24 mg QD.

[figure not shown]
Figure 3 Dose Adjustment Algorithm in the 12 to <18 Years Age Group

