### 4.3. Justification for Dose

In vitro studies have shown that isolated erythroid colony forming units from infants and adults have a similar quantitative response after stimulation by EPO [Rhondeau, 1988]. Similarly, the approved starting doses of rhEPO used to treat anemia associated with CKD are the same in adult and pediatric patients [Aranesp USPI, 2019; Epogen USPI, 2017]. It has been noted that during maintenance treatment of anemia, pediatric patients tend to require higher per kg doses than adult patients [KDIGO, 2012; KDOQI, 2006; Port, 2009], and this is reflected in data collected in the North American Pediatric Renal Transplant Cooperative Study [NAPRTCS, 2011], where the mean weight-normalized dose of rhEPO decreased over increasing age cohorts. Collectively, these data suggest the PK/pharmacodynamic relationship in children with CKD is not expected to be appreciably different to adult patients.

Due to the time-varying ontogeny in the drug metabolism of daprodustat as well as time-varying changes in body weight across age groups, a PBPK approach was utilized to estimate the potential starting doses for the different age groups using a validated PBPK model for daprodustat in healthy adults [GSK Document number 2019N396674\_00]. The PBPK model was derived using the Simcyp Pediatric Absorption Distribution Metabolism Excretion (ADME) Simulator which has 3 components to interrogate the known physiological and biochemical changes in a model to predict PK changes with age in healthy individuals [Abduljalil, 2014]. Therefore, doses for each age group are predicted by matching the pediatric systemic exposure (AUC) of daprodustat to that in adult.

The summary of estimated apparent clearance (dose/AUC) of daprodustat using PBPK in each age group is shown in Table 5, which also shows the predicted ratio of the pediatric to adult dose. Dose proportionality and time-independent PK is assumed when determining the doses in the pediatric population. It should be noted that although these predictions are for healthy individuals, daprodustat PK is generally similar between healthy individuals and renal impairment patients.

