#### CONFIDENTIAL

214066 Protocol Amendment 02

Table 5 Apparent Oral Clearance of Daprodustat by Age Group and Predicted Dose Equivalent to a 2 mg Adult Dose

Age Group	PBPK Model Weight Range Assumptions (kg)	CLpo (L/h) Geometric Mean	Dose (mg)	Ratio Pediatric to Adult Dose
Adults (≥18 years)	42.0 to 123.6	31.7	2	Not applicable
12 to <18 years	25.3 to 123.5	25.3	2	1/1
6 to <12 years	14.6 to 59.0	13.5	1	1/2
2 to <6 years	9.8 to 30.0	7.0a	0.5	1/4
3 months to <2 years	4.2 to 19.5	2.3ª	0.25	1/8

Abbreviations: CLpo = Apparent oral clearance

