## 9.3. Statistical Analyses

### 9.3.1. PK Analyses

#### During the study (Integrated PK Phase participants only):

In each sub-trial, the PK data (all available plasma concentration data) from each age group will be compared with the pre-specified PK simulations using the pediatric PBPK model. If more than 50% of the data lie outside the 95% PIs of the PK simulations, the PBPK model will be updated and simulations undertaken to determine the dosing (adult to pediatric ratio) to be used in the next younger age group.

A plot of the individual plasma PK concentration data overlaid with the PBPK model predictions will be provided.

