## 12.1. Sub-group Pharmacokinetic Analyses

Plasma daprodustat concentrations from each age group will be compared to predicted concentration-time profiles prior to enrolling the next younger age group into the study. If more than 50% of the daprodustat PK data does not lie within the pre-specified 95% prediction intervals of the PK simulations for the current age group, the PK data will be applied to update the physiologically-based pharmacokinetic (PBPK) SimCYP® model and undertake further simulations for time course of drug concentrations. GSK Clinical Pharmacology Modeling & Simulation (CPMS) and GSK Drug Metabolism & Pharmacokinetics (DMPK) will be responsible for the sub-group PK assessment.

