## 1.2. Analysis Rationale

The analysis described in the present Study Analysis Plan (SDAP) aims to:

- i) assess the daprodustat PK data emerging from the pediatric study, with the intention to describe the pharmacokinetics of daprodustat in adolescent participants who have evaluable PK data.
- ii) Considering that the study was stopped after enrolment of the first 4 adolescent participants, who were the only participants concluding the study, the analyses also aim to confirm the dosing regimen to be used in cohorts of subjects of adolescents. For this aim, the available daprodustat plasma concentrations (dosenormalized as required) will be projected in a plot together with the reference

Page 10 of 22

plasma concentrations observed in adult participants, defined *via* the PBPK simulation exercise (95%PI) [3]. If ≤50% of observations are outside the prespecified reference levels, the dose algorithm proposed for adolescents will be considered adequate. If instead >50% of observations are outside the prespecified reference levels, model-based simulations based on the population PK model and/or PBPK model may be performed to propose alternative starting dosing regimens, able to more appropriately match the exposures observed in adult participants. The adoption of the starting alternative dosing regimen should be sufficiently flexible considering i) the available dosing strengths, and that ii) daprodustat doses will be anyway modulated using the emerging Hemoglobin data.

This modelling exercise will concern the parent drug, daprodustat. As far as metabolites are concerned, a minimal contribution to daprodustat pharmacology cannot be excluded, but the available information indicate that metabolite contribution to clinical effects is minimal. Indeed, in a cocktail study in mice, the key metabolites of daprodustat showed negligible effect on haemoglobin, haematocrit, and red blood cell count compared to unchanged daprodustat. The PK of metabolites is thus considered out-of-scope in the modelling of paediatric data. Metabolite concentration data will be collected in the paediatric study, but they will simply be described using descriptive statistics.

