## 2. ANALYSIS OBJECTIVES

The overall objectives of these analyses are to:

- 1. Describe the pharmacokinetics of daprodustat in adolescent participants with CKD.
- 2. Provide support to the dosing regimen to be used in adolescent participants. Considering that the study enrolled only 4 participants in the adolescent age range, this assessment will be based on all participants (both D and ND subtrial/subpopulation)

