## 5.2. Confirmation of Dosing Regimen in Adolescent Participants

[figure not shown]
The criterion used for exploring the consistency between simulated data in adults and plasma concentration data in the available adolescents participants will be that >50% of the observed concentrations in the specified age group of pediatric participants is included in the 95% prediction intervals of the simulated data in adults at 2 mg.

The 95% prediction intervals of the simulated data in adults are shown in Figure 2 (together with simulated observations in a panel of 4 participants); 95% prediction intervals of adult daprodustat plasma concentrations following repeated dose of 2 mg are also reported in Table in the Appendix.

If the consistency between predicted and observed concentration data will be ensured (see Figure 2, where only 4 out of 16, i.e., 25% of the observed plasma concentrations are outside the predefined prediction intervals), the outcome of the previously defined pediatric simulations can be considered adequate. Therefore, it can be concluded that the dosing regimen proposed in adolescents (equivalent to that applied to adult participants) is reasonable. Based on this information, it might also be inferred that the starting dose foreseen by the protocol for participants 6-<12 years old (starting dose of 1 mg QD subsequently titrated based on hemoglobin levels) is reasonable.

If the consistency between observations and predictions will not be ensured, then the popPK model (see Section 5.1) may be used (after suitable modifications, as required) to propose a different dose to be used in adolescents and/or in participants in the lower pediatric age ranges.

Figure 2. Overlay of Simulated Daprodustat Plasma Concentrations in Virtual Pediatric Participants after Repeated Dosing of Daprodustat (Normalized to a Dose of 2 mg QD) on the 95% Prediction Interval of Daprodustat Plasma Concentrations in Adults [3].

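### The adolescent PK check uses an adult interval where the protocol uses a pediatric one, and its 50% rule would be expected to pass even a threefold exposure

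*Protocol*

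**What the plan says.** **Reference for the comparison.** Protocol 9.3.1 has the concentrations in each age group "compared with the pre-specified PK simulations using the pediatric PBPK model". SAP 12.1 refers to the "pre-specified 95% prediction intervals of the PK simulations for the current age group". The PK analysis plan, which follows the SAP in the same file, changes this. Its section 1.2 sets the reference as adult levels defined by PBPK simulation, and 5.2 asks whether more than half of the observed adolescent concentrations "is included in the 95% prediction intervals of the simulated data in adults at 2 mg".

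**Rule and conclusion.** Under PK plan 1.2, if no more than 50% of observations fall outside, "the dose algorithm proposed for adolescents will be considered adequate". Section 5.2 then treats the earlier pediatric simulations as adequate and the adolescent regimen as reasonable. It adds that the starting dose for 6 to <12 years might also be inferred to be reasonable. Objective 2 of the PK plan is to "Provide support to the dosing regimen to be used in adolescent participants".

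**Predicted adolescent exposure.** Protocol 4.3 defines apparent clearance as dose over AUC, assumes dose proportionality, and says "doses for each age group are predicted by matching the pediatric systemic exposure (AUC) of daprodustat to that in adult". Table 5 ("Apparent Oral Clearance of Daprodustat by Age Group and Predicted Dose Equivalent to a 2 mg Adult Dose") gives 31.7 L/h for adults and 25.3 L/h for 12 to <18 years, both at 2 mg, with a dose ratio of 1/1. The worst-case footnote marks only the two youngest groups. Section 4.5.1 then argues: "As exposure in the oldest age group (12 to <18 years) is predicted to be the same as adults".

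**The concern.** Two features of the PK plan weaken its conclusion, and a third point is wording.

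- A comparison with the adult interval asks whether adolescent concentrations look adult. It does not test the pediatric simulation, yet a pass is credited to that simulation.
- The adult interval is very wide at the pre-dose and late samples. A pooled count with a 50% allowance may therefore pass under large shifts in exposure.
- Table 5 and section 4.5.1 give different predictions for adolescents, so the expected value against which the result should be read is unclear.

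This is the planned PK assessment for the only age group enrolled. A reader of the PK report could take a pass as evidence of matched exposure when the rule is not able to show that.

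**Working it through.** **1. What Table 5 implies.** AUC = dose/CLpo.
- Adults: 2000 µg / 31.7 L/h = 63.1 ng·h/mL.
- 12 to <18 years: 2000 / 25.3 = 79.1 ng·h/mL.
- Ratio: 31.7/25.3 = 1.25.

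**2. Which population Appendix Table 2 of the PK plan describes.** The trapezoidal area under its median column, 0 to 24 h, is 66.4 ng·h/mL (taking ng/mL). That is near 63.1 and not 79.1, so the reference is the adult simulation, as its title states.

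**3. Width of the interval.** The ratio of the 97.5th to the 50th percentile in Table 2 is:
- pre-dose: 18
- 0.5 to 1.5 h: 2.6 to 3.1
- 1.5 to 3 h: 3.1 to 6.1
- 4 to 8 h: 10 to 30

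**4. Expected share outside if all concentrations are multiplied by k.** At each time I take a split log-normal through the 2.5th, 50th and 97.5th percentiles (L, M, U):
- P(above U) = 1 − Φ(1.96 × [1 − ln k / ln(U/M)])
- P(below L) = 1 − Φ(1.96 × [1 + ln k / ln(M/L)])

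Example at 1 h with k = 3: ln 3 = 1.099 and ln(73.11/27.78) = 0.968, so P(above) = 1 − Φ(−0.265) = 60%. At 6 h: ln(12.87/0.558) = 3.137, so P(above) = 1 − Φ(1.274) = 10%. P(below) is about 0.1% or less at both times.

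Times are uniform within each window, and the four windows are weighted equally:

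| k | pre-dose | 0.5–1.5 h | 1.5–3 h | 4–8 h | all four | post-dose only |
|---|---|---|---|---|---|---|
| 1 | 5% | 5% | 5% | 5% | 5% | 5% |
| 1.25 | 5% | 7% | 6% | 5% | 6% | 6% |
| 2 | 8% | 26% | 16% | 7% | 14% | 17% |
| 3 | 11% | 54% | 32% | 11% | 27% | 32% |

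The expected share reaches 50% at k of about 6.3 (about 4.8 counting post-dose samples only).

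**5. Probability of a pass at k = 3.** For four participants with four samples each and within-participant correlation 0 to 0.9, simulation gives 0.94 to 0.99 when up to 8 of 16 may lie outside. It gives 0.88 to 0.97 when at most 7 may.

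**6. The two statements of the rule.** Section 1.2 passes at no more than 50% outside. Section 5.2 needs more than 50% inside. With exactly 8 of 16 outside, the first passes and the second does not.

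**7. Sensitivity.** A symmetric log-normal gives 24% outside at k = 3, with 50% at about 6.3 (about 5.1 post-dose only). A rough model in which clearance falls to a third and the curve changes shape gives about 28%.

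**8. What a ratio from four participants could show.** Taking the adult reference as fixed, the 95% CI factor is exp(3.182 × s/√4), with s² = ln(1 + CV²) summed over CL and F1. The CVs are from Appendix Table 1 of the PK plan.
- CL 15.9% and F1 26.3%: s = 0.303, factor 1.62.
- CL 75.0%, no F1 term: s = 0.668, factor about 2.9.

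Both exceed 1.25. Residual error and sparse sampling would widen them.

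**The case against.** **The rule was not built as a test.** In the protocol the 50% criterion triggers an update of the PBPK model. It sits beside Hgb, safety and IDMC review, in a study with no formal hypotheses (9.1). This is fair, and 5.2 of the PK plan speaks only of exploring consistency. But 1.2 attaches a finding of adequacy to the same count, so the narrower criticism stands.

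**An adult reference is defensible**, because the programme aims to match adult exposure, and a 1.25 shift barely changes the count (5% to 6%). SAP 2.1 and 3.2.3 also assign PK methods to a separate document, so silence in SAP 14 means little. All true. What remains is that the PK plan does not explain the change either, and that an adult comparison cannot validate a pediatric simulation.

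**The 1.25 is rounding.** Table 5 uses halving ratios throughout, and 4.5.1 goes on to call the algorithm similar to adults. That explains the 1/1 ratio but does not make the predicted exposures equal. Enrolment has ended, so this is now the least consequential part.

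**Much is already planned.** Cmax, AUC and their geometric means are in the PK estimand, and post-hoc estimates, diagnostic plots and an overlay are in the PK plan. What is missing is the ratio with its interval.

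**An alternative shares the weakness.** Post-hoc estimates start from an adult-based model without re-estimation (PK plan 5.1) and may shrink towards it. This stands and shapes the fix.

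**Stronger readings to avoid.** A reader might infer that adolescents are overexposed or at risk. The documents do not support that: doses are titrated to Hgb, and 1.25 may well be acceptable. A reader might also treat 4 of 16 outside in the plan's example as evidence of misfit. Figure 2 is labelled as simulated virtual participants, so it is an illustration and not data.

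**Conclusion.** The concern holds for the PK plan. Its reference differs, without explanation, from Protocol 9.3.1 and SAP 12.1. A pass is credited to pediatric simulations that the comparison does not test. The rule would be expected to report adequacy at 1, 1.25, 2 or 3 times adult concentrations, since a pooled share of 50% outside needs about a 6.3-fold shift (about 5-fold post-dose only).

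The rule is not blind everywhere. At threefold, the 0.5 to 1.5 h window alone would put about half of its samples outside, and the wide pre-dose and late intervals dilute this. The inference to 6 to <12 years is hedged in the plan and should not be read as a firm conclusion.

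These figures assume linear PK, a uniform multiplier and a log-normal shape drawn from three percentiles. The alternatives tried lead to the same answer. The 1.25 is derived from Table 5, not printed. The point is worth acting on but modest: it concerns what the PK report may claim, not study conduct or safety.

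**What to change.** - State which reference interval is used, and reconcile Protocol 9.3.1 and SAP 12.1 with PK plan 1.2 and 5.2. Overlay both intervals where the pediatric output exists; PK plan 1.1.1 indicates that pediatric simulations were run.
- Use one form of the 50% rule, so that exactly half outside has a single outcome.
- Report the share outside by sampling window as well as pooled.
- Beside the count, give each adolescent's dose-normalised steady-state AUC and Cmax, and the geometric mean ratio to adults with a 95% CI. Show the AUC ratio against 1.00 and the 1.25 implied by Table 5. Report shrinkage. A CI of about ×/÷1.6 to ×/÷2.9 will not separate those two values, but it shows how little four participants can say.
- Limit the conclusion to what that interval supports, and do not call the pediatric simulations adequate on an adult comparison.
- Reconcile Protocol 4.3 and Table 5 with 4.5.1.

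The cost is some wording, one overlay and one small table from estimates already planned, with no new data. The downside is a less favourable-sounding conclusion. No dose or dosing threshold is proposed.

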## 4.5.2. Dose Adjustment Algorithm in the Younger Age Groups

A common dose adjustment algorithm will be utilized for the 3 younger age groups, see Figure 4.

Figure 4 Dose Adjustment Algorithm in the Younger Age Groups (<12 years)

Abbreviations: m = months; PBPK = physiological based pharmacokinetics; TfOS = tablets for oral suspension; y = years.

214066 Protocol Amendment 02

These dose steps (shown in Figure 4) for the 3 younger age groups are derived by applying the adult to pediatric ratio from the PBPK model to the dosing steps for adults (see Table 9) and then lining up the doses in ascending order. This is a conservative approach, and in some cases may mean a slightly smaller dose increment than the predicted to match adult exposure, e.g., a 6 to <12 year old moves between 0.5 to 0.75 to 1 mg in a common dose algorithm rather than between 0.5 to 1 mg (see Table 9). No age group has a larger step than adult equivalent titration.

Table 9 Dose Adjustment Algorithm Predicted by the PBPK Model

Age Group	Ratio pediatric to adult dose	Dose steps predicted by the PBPK model (mg QD)							
12 <18 years	1/1	1	2	4	6	8	12	16	24
6 <12 years	1/2	0.5	1	2	3	4	6	8	12
2 <6 years	1/4	0.25	0.5	1	1.5	2	3	4	6
3 months <2 years	1/8	0.125	0.25	0.5	0.75	1	1.5	2	3

## Dosing Limits of the Common Dose Adjustment Algorithm for the 3 Younger Age Groups:

The upper limit of dosing in each of the 3 younger age groups can be considered based upon the following:

- PBPK predicted equivalent exposure to adult dose of 24 mg in each age group (see Table 9 or scaling adjusted as a consequence of an Integrated PK Phase), and
- maximum dose based on the limit on the number of tablets with a TfOS formulation (see Table 10 and also Section 6.1 for the TfOS limits per age group).

If ongoing data suggests that a pediatric population needs a higher dose than that predicted by the PBPK model in the younger age groups to match the top dose (24 mg) in adults, the IDMC **may** allow the dosing algorithm upper limit for the 3 younger age groups to include extra (higher) dose steps than the top dose predicted by the PBPK model. However, the maximum dose in each age of the younger age groups cannot exceed the limit on the number of tablets with a TfOS formulation (see Table 10).

214066 Protocol Amendment 02

Table 10 Extra Dose Steps for the Younger Age Groups based on TfOS Excipient Limits

Age Group	Top dose predicted by the PBPK Model from Table 9 (mg QD)	Maximum dose permitted with TfOS see Section 6.1 (mg QD)	Extra dose steps that may be included in the dosing algorithm above the PBPK model top dose prediction if the IDMC allow  (mg QD)
6 <12 years	12	16	16
2 <6 years	6	12	8, 12
3 months <2 years	3	8	4, 6, 8

As described in Section 4.4.2 for the starting dose, if a new scaling (pediatric to adult ratio) is required based on the results of an Integrated PK Phase, the new ratio will be applied to adjust the upper/lower dose limits of the common dose algorithm for the next younger age group (the dose steps within the algorithm will remain unchanged). Note: the new dose limits may be rounded to the nearest available tablet strength if new scaling is required.

It will be the responsibility of the IDMC to confirm the dosing strategy (starting dose and dose adjustment algorithm upper/lower limits) in each of the 3 younger age groups (see also Section 4.7), based on the following:

- pediatric to adult dose scaling predicted by the PBPK model (confirmed or as adjusted by the actual PK data collected), and also
- taking into account the ongoing knowledge of the:
  - Hgb response and safety from the 4 week Integrated PK Phases from each age group in each sub-trial (ND/D).
  - Overall Hgb and safety data from each sub-trial to date.

Note: Participants, who with a birthday move into the next age group during the course of the 52-week treatment period, will be allowed to be dosed (if required based on Hgb response, see Table 11) to the dosing limits defined for their current age, provided they weigh the minimum weight for that new age group, as specified in Table 12. For example:

- A participant aged 5 years 9 months at study enrollment cannot be dosed higher/lower than the limits set by the IDMC for a 2 to <6 year old. However, after their 6th birthday, their upper/lower limits of the dosing algorithm will move to their new age category of 6 to <12 years) provided they weigh at least 15.3 kg.
- A participant aged 11 years 9 months at study enrollment cannot be dosed higher/lower than the limits set by the IDMC for a 6 to <12 year old. However, after their 12th birthday, they will then follow the dosing algorithm of the 12 to <18 years old provided they weigh at least 25.3 kg and are able to swallow IR tablets, otherwise they must remain in the 6 to <12 years age group algorithm taking the TfOS.

214066

Protocol Amendment 02

Interactive Response Technology (IRT) will ensure the participant receives the correct dose allocation in case of an age group change. As age is required to allow correct dispensing of study medication, month and year of birth will be collected at enrollment.

CONFIDENTIAL

## 4.6. Hemoglobin Target Range and Frequency of Checks

In adults, the dose of daprodustat is adjusted if required, one step at a time in the range of 1 to 24 mg, to ensure the patient's Hgb is within a target range.

In this study, the target range for Hgb is 10 to 12 g/dL, the same for all ages and regardless of dialysis status (ND or D) or within the D sub-trial population, their dialysis modality (PD or HD).

For pediatric patients, nephrologists dose adjust ESA therapy in accordance with both Hgb and clinical response. At Study Weeks 2, 4, 8, 12, 16, 20, 24, 28, 36, 44 and 52, the Hgb will be checked.

